2.1.4.2 Deaths

The deaths per the observation period will be summarized.

- Death on-treatment: deaths occurring during the treatment period (i.e., treatment Epoch)
- Death during follow-up: deaths occurring during the residual treatment period
- Death post-treatment: deaths occurring during the post-treatment period

2.1.4.3 Laboratory safety variables

Clinical laboratory data will include hematology, clinical chemistry, and urinalysis. Clinical laboratory values will be converted to standard international units; international units will be used in all listings and tables. In addition, the lipids parameters will also be summarized in US units.

Hematology and chemistry data will be collected at screening, baseline, Weeks 4,12, 24, 40, and 52, and/or early termination unless otherwise specified. The laboratory parameters will be classified as follows:

- Hematology
 - **Red blood cells and platelets and coagulation:** hemoglobin, hematocrit, platelet count, red blood cell (RBC) count, and RBC morphology (if RBC count is abnormal).
 - **White blood cells:** white blood cell (WBC) count and WBC differential (neutrophils, lymphocytes, monocytes, basophils, eosinophils).
- Clinical chemistry
 - **Metabolism:** fasting lipids (total cholesterol, high density lipoprotein cholesterol (HDL-C), low density lipoprotein cholesterol (LDL-C), ratio of HDL-C versus LDL-C (HDL-C:LDL-C), triglycerides), total proteins, CRP, fasting glucose, and hemoglobin A1c (HbA1c).

- **Electrolytes:** sodium, potassium, chloride, calcium, phosphate, and bicarbonate.
- **Renal function:** creatinine, creatinine clearance, uric acid, and blood urea nitrogen (BUN).
- **Liver function:** alanine aminotransferase (ALT)/SGPT, aspartate aminotransferase (AST)/SGOT, alkaline phosphatase (ALP), albumin, total bilirubin, conjugated and unconjugated bilirubin, and lactate dehydrogenase (LDH).
- **Pregnancy test:** Serum β -hCG for all women of childbearing potential (screening only).
- **TB screen:** QuantiFERON®-TB Gold evaluation.
- **Hepatitis screen:** Hepatitis B and C serology, human immunodeficiency virus serology.

Urine samples will be collected as follows:

- **Urinalysis - dipstick:** pH, specific gravity, blood, glucose, protein, nitrates, leukocyte esterase, and bilirubin. If any parameter on the dipstick is abnormal, a urine sample was to be sent to the central laboratory for testing.

A urine pregnancy test was done for all women of childbearing potential at baseline, all visits up to Week 52 or early termination.

2.1.4.4 Vital signs variables

Vital signs variables include heart rate, systolic blood pressure, and diastolic blood pressure, height, weight, and body temperature.

2.1.4.5 Antinuclear antibodies

Antinuclear antibodies (ANA) will be measured at baseline and EOT visits.

2.1.5 Immunogenicity endpoints

The immunogenicity blood samples will be collected before injection during the same visit according to the Study Flow Chart ([Appendix A](#)).

Samples analyzed in the antidrug antibody (ADA) assay will be categorized as either positive or negative, and in the case of a positive result will be further characterized as either neutralizing or non-neutralizing.

ADA positive patient is defined as patient with at least one treatment-emergent or treatment-boosted ADA positive sample during the TEAE period, where

- Treatment-emergent ADA positive patient is defined as a patient with non-positive assay (meaning negative or missing) response at baseline but with a positive assay response during the TEAE period.
- Treatment-boosted ADA positive patient is defined as a patient with a positive ADA assay response at baseline and with at least a 4-fold increase in titer compared to baseline during the TEAE period.

ADA negative patient is defined as patient without a treatment-emergent or treatment-boosted ADA positive sample during the TEAE period.

A treatment-emergent positive response is further classified as persistent or transient.

Persistent ADA response: treatment-emergent ADA detected at two or more consecutive sampling time points during the TEAE period, where the first and last ADA positive samples are separated by a period of at least 16 weeks. Also persistent in case last sample analyzed is positive.

Transient ADA response: A treatment-emergent response that is not determined to be persistent.

2.1.6 Pharmacokinetic variables

The blood samples for the determination of functional sarilumab concentrations in serum will be collected before injection during the same visit according to the Study Flow Chart (refer to Section 1.2 in the study protocol) and at or near the onset and completion of the occurrence of a SAE.

2.1.7 Pharmacodynamic/genomics endpoints

Blood samples (DNA and genetic RNA) will be collected from each consenting patient to participate in the pharmacogenomics substudy. Details of any analysis will be described in a separate plan.

2.1.8 Other efficacy endpoints

Quality-of-life endpoints

Other efficacy endpoints in the clinical outcome assessments will be summarized. Patients are asked to complete the following patient-reported outcome (PRO) questionnaires described below at Visit 2 (baseline visit), Visit 6 (Week 12), Visit 9 (Week 24), and Visit 12 (Week 52).

Patient-Reported Outcomes

Short Form 36 Version 2 (SF-36 V2)

The SF-36 V2 is a multi-purpose, short-form health survey with 36 questions. It yields scores for eight domains (Physical Functioning, Role-Physical, Bodily pain, General health, Vitality, Social Functioning, Role-Emotional, and Mental Health, each scale is scored from 0 to 100 where higher scores indicate better health and well-being), as well as two summary measures of physical and mental health: the Physical Component Summary (PCS) and Mental Component Summary (MCS).

The scoring process is summarized below:

- Enter item response data.
- Recode item response values.
- Determine health domain scale raw scores.
- Transform health domain scale raw scores to 0 to 100 scores.
- Transform health domain scale 0 to 100 to normal-based scores.
- Score physical and mental component summary measures.

The following table shows the construction and summary measures of the SF-36 scales:

Table 6 - SF-36 V2 measurement model

Summary measures	Scales	Items
Physical Component Summary (PCS)*	Physical Functioning (PF)	3a, 3b, 3c, 3d, 3e, 3f, 3g, 3h, 3i, 3j
	Role-Physical (RP)	4a, 4b, 4c, 4d
	Bodily Pain (BP)	7, 8
	General Health (GH)	1, 11a, 11b, 11c, 11d
Mental Component Summary (MCS)*	Vitality (VT)	9a, 9e, 9g, 9i
	Social Functioning (SF)	6, 10
	Role-Emotional (RE)	5a, 5b, 5c
	Mental Health (MH)	9b, 9c, 9d, 9f, 9h

*MCS and PCS derived from the eight scales

The score of each of the 36 items is collected in CRF. [Appendix G](#) provides the SAS code to calculate the eight scales, the two summary measure scores and the standardized summary scores.

The PCS and MCS summary measure scores will be computed if at least 50% of the component scales are available. The scale scores will be computed if at least 50% of items are available within the corresponding scale. The missing items will be imputed by the mean of available items.

Change from baseline in SF-36 scores (physical component summary score and mental component summary score as well as the eight domains) at each visit will be analyzed.

Functional Assessment of Chronic Illness Therapy Fatigue (FACIT-Fatigue)

The FACIT-Fatigue will be used to assess fatigue. The FACIT-Fatigue is a 13-item questionnaire rated 0 to 4 originally developed to measure fatigue in patients with cancer and is widely used in rheumatoid arthritis patients to demonstrate good consistency and sensitivity to change. The patient will be asked to answer 13 questions rated 0 to 4 (0 = not at all, 1 = a little bit, 2 = somewhat, 3 = quite a bit, 4 = very much). The fatigue scale has 13 items, with 52 as the highest possible score. A higher score in the fatigue scale corresponds to a lower level of fatigue and indicates better Quality of Life.

To calculate the FACIT-fatigue score, the response scores on negatively phrased questions are reversed and then the 13 item responses are added. Eleven items with responses have their scores reversed (item score = 4 – response, if the response is not missing), and two items (items 7 and 8) have their responses unchanged ([Appendix E](#)). All items are added so that higher scores correspond to less fatigue. In cases where individual questions are skipped, scores are prorated using the average of other answers in the scale.

FACIT-Fatigue = 13 * [sum (reversed items) + sum (items 7 and 8)] / number of answered items

EuroQol 5 Dimension 3 Level (EQ-5D-3L)

The EQ-5D-3L is a standardized, generic measure of health outcome (3). EQ-5D is designed for self-completion by patients. Instructions to respondents are included in the questionnaire. The EQ5D is specifically included to address concerns regarding the health economic impact of RA, which have been considered in cost effectiveness arguments. The EQ-5D-3L comprises five questions on mobility, self-care, pain, usual activities, and psychological status with three possible answers for each item (1 = no problem, 2 = moderate problems, 3 = severe problems) and a vertical visual analog scale that allows the patients to indicate their health state today that can range from 0 (worst imaginable) to 100 (best imaginable).

The 5 dimensional 3-level systems are converted into a single index utility score. Values for the 243 theoretically possible health states defined by the EuroQol classification are calculated using a regression model and weighted according to the social preferences of the GB population. The minimum value for the single index utility score is -0.594, which corresponds to a level 3 (severe problems) for mobility, self-care, usual activities, pain/discomfort and anxiety/depression. The maximum value for this index is 1.0, which corresponds to a full health (level 1 [no problem] for mobility, self-care, usual activities, pain/discomfort and anxiety/depression).

The VAS records the respondent's self-rated health on a vertical visual analogue scale. The VAS "thermometer" has endpoints of 100 (Best imaginable health state) at the top and 0 (Worst imaginable health state) at the bottom. This information can be used as a quantitative measure of health outcomes as judged by the individual respondents. EQ 5D self-reported VAS data generates information on the self-perceived overall health-related quality of life.

[Appendix F](#) provides the SAS code to derive the index utility score using GB based population.

Health Assessment Questionnaire Disease Index (HAQ-DI)

• Patient's Assessment of Physical function

The HAQ-DI is a standardized questionnaire developed to assess physical functional status in adults with arthritis but is now commonly used among many rheumatologic conditions. The HAQ-DI, with the past week as the time frame, focuses on whether the respondent “is able to...” do the activity and covers eight categories in 20 items: dressing and grooming, arising, eating, walking, hygiene, reach, grip and activities, for which there are at least two questions by category. The four responses for the HAQ-DI questions are graded as follows: without any difficulty=0; with some difficulty=1; with much difficulty=2; and unable to do=3. To calculate the Standard HAQ-DI Score (With Aids/Devices), there are 3 steps:

1. Sum the eight category scores by using the highest sub-category score from each category.
 - For example, in the category EATING there are three sub-category items. A patient responds with a 1, 2, and 0, respectively; the category score is 2.
2. Adjust for use of aids/devices and/or help from another person when indicated.
 - When there are NO aids or devices or help indicated for a category, the category's score is not modified.
 - When aids or devices or help ARE indicated by the patient:
 - Adjust the score for a category by increasing a 0 or a 1 to a 2.
 - If a patient's highest score for that sub-category is a 2 it remains a 2, and if a 3, it remains a 3.
 - The data entered at field “Other specify” will not be used for score adjustment.
3. Divide the summed category scores by the number of categories answered (must be a minimum of 6) to obtain a HAQ-DI score of 0 to 3 (3=worst functioning).

A HAQ-DI score cannot be calculated validly when there are scores for less than six of the eight categories. If there are less than 6 categories completed, a HAQ-DI cannot be computed, whether the missing categories are due to missing values or they do not apply to the respondent. HAQ-DI disability index scoring ranges between 0 and 3 with higher score indicating greater disability. A high HAQ-DI score has been found to be a strong predictor of morbidity and mortality in RA. A 0.22 unit difference is considered clinically meaningful.

In addition to the above, the HAQ-DI has two additional questions to measure pain and global assessment described below.

• Patient's Assessment of Pain

Patients will be requested to indicate their pain intensity due to PMR using a 100 mm horizontal VAS to the question “*How much pain have you had IN THE PAST WEEK?*”, where 0 is considered “No pain” and 100 “the worst pain you can imagine”.

To obtain the patient score, using a metric ruler, measure the distance in centimeters from the left anchor (at base zero) to their mark and multiply by 0.2. This converts the number of centimeters into the appropriate score and yields a score from 0 to 3. For example, the mark is at 8 centimeters – $8 \times 0.2 =$ a pain score of 1.6.

In case a 0-100 mm scale is used, pain severity coding translations follow below:

PAIN SEVERITY CODING TRANSLATIONS

Measurement (m) = Score	Measurement (m) = Score [continue]
0 = 0	7.8 - 8.2 = 1.6
0.1 - 0.7 = 0.1	8.3 - 8.7 = 1.7
0.8 - 1.2 = 0.2	8.8 - 9.2 = 1.8
1.3 - 1.7 = 0.3	9.3 - 9.7 = 1.9
1.8 - 2.2 = 0.4	9.8 - 10.2 = 2.0
2.3 - 2.7 = 0.5	10.3 - 10.7 = 2.1
2.8 - 3.2 = 0.6	10.8 - 11.2 = 2.2
3.3 - 3.7 = 0.7	11.3 - 11.7 = 2.3
3.8 - 4.2 = 0.8	11.8 - 12.2 = 2.4
4.3 - 4.7 = 0.9	12.3 - 12.7 = 2.5
4.8 - 5.2 = 1.0	12.8 - 13.2 = 2.6
5.3 - 5.7 = 1.1	13.3 - 13.7 = 2.7
5.8 - 6.2 = 1.2	13.8 - 14.2 = 2.8
6.3 - 6.7 = 1.3	14.3 - 14.7 = 2.9
6.8 - 7.2 = 1.4	14.8 - 15.0 = 3.0

- ***Patient’s Global Assessments of Disease Activity***

Patient’s global assessments of their current disease activity will be rated on an anchored 100 mm horizontal VAS, with the given instruction to “*Please rate how well you are doing on a scale of 0 to 100 (0 represents “very well” and 100 represents “very poor” health)*”.

It is scored similarly to the VAS Pain Scale.

Clinician-Reported Outcomes

Physician’s Global Assessments of Disease Activity - Visual Analog Scale [MD-VAS]

Physician’s global assessments of the patient’s current disease activity will be assessed on an anchored 100 mm horizontal VAS where 0 is considered the best disease activity (no disease activity) and 100 the worst (most disease activity).

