2.4.7 Analyses of quality of life variables

Descriptive statistics including number of subjects, mean, median, SD, minimum, maximum will be provided by treatment groups for the value and change from baseline at each visit (baseline, Week 12, Week 24 and Week 52) for the 2 summary measures of SF-36 (physical component summary score and mental component summary score) and the 8 domains, the quantitative variables of EQ-5D-3L (visual analog scale and single index utility), FACIT-Fatigue, HAQ-DI (standardized score, pain score and patient global assessment) and MD-VAS. Analyses will be performed based on data as observed; no missing data will be imputed.

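### SAP 2.1.8 scores HAQ-DI pain at 0.2 per cm and states a 0 to 3 range, but on its own 100 mm line the rule and its table stop at 2.0

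*SAP*

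**What the plan says.** In SAP 2.1.8, under the HAQ-DI, the patient rates pain "using a 100 mm horizontal VAS to the question" about the past week. To score it, the analyst is to "measure the distance in centimeters from the left anchor (at base zero) to their mark and multiply by 0.2". The SAP adds: "This converts the number of centimeters into the appropriate score and yields a score from 0 to 3". The worked example ("For example, the mark is at 8 centimeters") arrives at 1.6.

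A coding table follows, introduced as the one to use with a 0 to 100 mm scale. It gives 2.0 for 9.8 to 10.2 and continues to 3.0 for 14.8 to 15.0.

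Patient global assessment "will be rated on an anchored 100 mm horizontal VAS", and "It is scored similarly to the VAS Pain Scale". The physician's global assessment (MD-VAS), on the same line length, "will be assessed on an anchored 100 mm horizontal VAS where 0 is considered the best disease activity" and 100 the worst, with no conversion.

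SAP 2.4.7 then summarizes "HAQ-DI (standardized score, pain score and patient global assessment) and MD-VAS" together, by value and change from baseline, without naming the scale of any of them.

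The protocol puts both extra HAQ-DI questions on 0 to 100 scales (9.3.1.1.4), and both lines in Appendix H end at 100 mm. SAP 1.6, which lists the changes from the protocol's analysis, mentions no rescaling of these items.

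**The concern.** The line length, the multiplier and the stated range cannot all be right. The rule, its example and its table agree with one another, and together they fit a line of 15 cm. The SAP, the protocol and the questionnaire appendix all describe a line of 10 cm.

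These items are reported only as descriptive values and changes, so the printed numbers are the result. A reader told that pain is scored 0 to 3 would take 2.0 as one third short of the maximum, when it is the worst answer a patient can give. Patient global, if scored the same way, would run 0 to 2 beside an MD-VAS that runs 0 to 100. As SAP 2.4.7 names no scale, a programmer could defend 0 to 2, 0 to 3 or 0 to 100.

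**Working it through.** **Inputs**

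- Line length: 100 mm = 10 cm (SAP 2.1.8; Protocol 9.3.1.1.4 and Appendix H agree).
- Rule: score = distance in cm × 0.2 (SAP 2.1.8).
- Stated range: 0 to 3 (SAP 2.1.8).
- Worked example: 8 cm gives 1.6 (SAP 2.1.8).
- Table: 9.8 to 10.2 gives 2.0; last row, 14.8 to 15.0, gives 3.0 (SAP 2.1.8).

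**Reproducing the SAP's own figures**

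- Example: 8 × 0.2 = 1.6. It reproduces.
- Range: the maximum on the line is 10 × 0.2 = 2.0, so the stated maximum of 3 does not reproduce.
- Line length needed for 3.0: 3 / 0.2 = 15 cm.
- Table: every legible row from 0.8 cm upward agrees with cm × 0.2 to rounding. The highest row reachable at or below 10.0 cm is 2.0. The ten rows from 2.1 to 3.0 cannot be reached.

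The table header gives its unit as (m), which may be a PDF-reading fault, so I read the entries as centimetres. Reading them as millimetres would not help, because the table would then cover only 0 to 15 mm.

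**Factor that would give 0 to 3 on a 10 cm line**

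3 / 10 = 0.3 per cm (0.03 per mm). The SAP's factor relative to this is 0.2 / 0.3 = 0.667.

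| Mark or change | SAP rule (× 0.2) | True 0 to 3 score (× 0.3) |
|---|---|---|
| 100 mm | 2.0 | 3.0 |
| 80 mm | 1.6 | 2.4 |
| 50 mm | 1.0 | 1.5 |
| 20 mm change | 0.4 | 0.6 |

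The SAP's example therefore places a mark at 80% of the line at 1.6 / 3 = 53% of the stated maximum.

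**Using the table instead of the multiplication**

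The 101 whole-millimetre marks from 0 to 100 fall into 21 scores, 0 to 2.0 in steps of 0.1. This count takes the row for 7.3 to 7.7 (score 1.5) as present; it is missing from the text I have, possibly lost in PDF reading. In the 0.1 to 0.7 row the table differs from cm × 0.2 by up to 0.08 (a 1 mm mark scores 0.1 against 0.02). Above that row it differs by up to 0.04 (72 mm scores 1.4 against 1.44).

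**The case against.** The arithmetic is not in dispute. The case on the other side concerns consequence and interpretation.

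- **Little depends on it.** Pain and patient global are other efficacy endpoints, and SAP 2.4.7 plans no test, model or imputation for them. The trial stopped at 83 of 360 planned patients. A constant factor alters neither the direction nor the standardized size of a contrast. This stands, and it keeps the point from being a major one.
- **The rule may never be used.** Appendix H is a paper form to be adapted for electronic capture, where a metric ruler has no obvious role. That is a fair reason for doubt, and the effect stated here is conditional on the rule being applied. It is also a further reason to remove the rule and keep 0 to 100.
- **Perhaps only the stated range is wrong.** The multiplier, the example and the 2.0 row agree, so the scores could be read as correct on a mislabelled 0 to 2 scale. Relabelling would make the text consistent. It would also produce a range that neither document states for these items, and the surplus table rows would still have to go.
- **No data are lost.** Protocol 10.3 lists the HAQ-DI and its VAS as source data, so the original marks survive. That is correct. The loss from binning concerns the derived score only: exact 0 to 100 values cannot be worked back from it.
- **MD-VAS need not share a scale with patient items.** True. The comparison matters only because the three are listed together with no scale named.

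**Conclusion.** The concern holds. On the 100 mm line that the SAP itself specifies, the pain score runs from 0 to 2.0, not 0 to 3, under both the multiplication rule and the table. If the rule is applied, reported means, SDs and changes are 0.667 of a true 0 to 3 score. Patient global is affected to the same degree, assuming that similar scoring there means the same rule.

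The result rests on the line being 10 cm, on which both documents agree, and on the table entries being centimetres. It does not depend on the missing table row, which affects only the count of 21 scores.

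The primary endpoint and the HAQ-DI disability score are untouched. This should be corrected before the tables are programmed, but it does not threaten the trial's conclusions.

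**What to change.** Report pain and patient global on the 0 to 100 scale of Protocol 9.3.1.1.4 and Appendix H, which the SAP already keeps for MD-VAS. In SAP 2.1.8, delete the 0.2 conversion, the worked example and the table running to 15.0.

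Only if a 0 to 3 score is kept instead, use 0.3 per cm (0.03 per mm), correct the example to 8 cm = 2.4, and still delete the table.

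In either case, state in SAP 2.4.7 which scale is summarized, separately for pain and for patient global.

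The cost is SAP wording and one line of derivation code. No new data are needed.

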2.2 DISPOSITION OF PATIENTS

This section describes patient disposition for both patient status and the patient populations.

Screened patients are defined as all patients who signed the informed consent.

Randomized patients consist of all patients who signed informed consent with a treatment kit number allocated and recorded in the Interactive Voice Response System/Interactive Web Response System database, regardless of whether the treatment kit was used or not.

For patient status in the DB treatment period, the total number of patients for each one of the following categories will be presented in the clinical study report (CSR) using a summary table:

- Screened patients
- Screen failure patients and reasons for screen failure
- Non-randomized but treated patients
- Randomized patients
- Randomized but not treated patients
- Randomized and treated patients
- Patients who completed SC IMP treatment up to Week 24
- Patients who discontinued SC IMP treatment before Week 24 and the reasons for permanent treatment discontinuation
- Patients who completed 52-week SC IMP study treatment period
- Patients who discontinued from 52-week study treatment period and the reasons for permanent SC IMP treatment discontinuation
- Patients who completed the study
- Patients who discontinued the study and the reasons for study discontinuation
- Patients who took CS rescue therapy
- Subject status at end of study visit

For all categories of patients (except for the screened and non-randomized categories) percentages will be calculated using the number of randomized patients as the denominator. Reasons for discontinuation with regards to SC IMP treatment will be presented in tables giving numbers and percentages by treatment group.

A patient is considered as lost to follow-up at the end of the study if he/she is not assessed at the end of study visit.

All critical or major deviations potentially impacting efficacy analyses, randomization and drug dispensing irregularities and other major/critical deviations will be summarized in tables giving numbers and percentages of deviations by treatment groups.

Additionally, the analysis populations for safety, efficacy, PK, and immunogenicity will be summarized in a table by patient counts based on the randomized populations (See definitions in [Section 2.3](#)).

- Efficacy population

- Safety population
- PK population
- ADA population

